- light walking around chair or in a circle: 3 circles

Stretches in standing position (with or without a chair) (≈ 15 min)

- a variety of lower-extremity muscle stretching and flexibility exercises that include:
 - quadriceps (thigh) stretch, hamstring stretch, calf stretch, ankle pivoting, circling, and stretch
- light walking around chair or in a circle: 3 circles

Stretches in chair (≈ 10 min)

- a variety of lower-extremity muscle stretching and flexibility exercises that include:
 - quadriceps (thigh) stretch, hamstring stretch, calf stretch, ankle pivoting, circling, and stretch

Stretches while moving around (≈ 8 min)

• a variety of upper- and lower-extremity and trunk stretching exercises in standing position, which may involve slow bending (forward, sideways), reaching (arm forward or upward, or sideways), and turning (one half-circle – 180 degrees)

Instructions: pay attention to the following:

- range of motion (ROM): slow progression from 50% to 80%-90% ROM
- repetitions: 3 reps of each stretch and held to the point of mild tension for 5 seconds
- rotation: if an exercise involves a rotation, repeat 3 times on each side
- circle: if an exercise involves circling (e.g., ankle), repeat 3 times
- · breathe naturally throughout the stretch

Winding-down (≈ 2 min)

• Seated or standing: light breathing and relaxing (meditative, verbal cued whole body) exercises - may repeat some of the warm-up exercises

Adverse events monitoring

Throughout the study period, both intervention- and non-intervention-related adverse events will be closely monitored and recorded by research staff and adjudicated by the Principal Investigator of the study. We will classify adverse events in three categories: Mild, Moderate, and Serious. Similarly, for all events observed or reported in this study, we will further classify them into three categories in relation to the intervention: Unrelated, Possible, or Definite. The following section describes the classification and categorization of our study adverse events. Per our IRB protocol, any serious adverse events will be reported to the IRB and the project Safety Officer within 48 hours of the reported incident.

Adverse Event and Serious Adverse Event Collection Process

The project defines Adverse Events and Serious Adverse Events as follows:

Definition of Adverse Events may include the following:

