- Any musculoskeletal pain or discomfort, including lower back pain, ankle/muscle soreness or pain, or a fall without needing medical attention
- Any event that requires medical treatment but is not an immediate life-threatening condition (e.g., eye surgery or a medical procedure)

Definition of Serious Adverse Events are undesirable experiences associated with the prescribed exercise interventions in this project. Serious Adverse Events may include the following:

- Death
- Falls that result in a serious injury that requires immediate medical attention
- Prolonged hospitalization
- Important medical or life-threatening events such as a heart attack that require treatment in an emergency room
- Events that cause persistent or significant disability or incapacity

Classification of Adverse Events

This project will classify any adverse events observed during the 6-month active exercise intervention period into the following three categories:

- Mild: events that require no medical treatment or are non-life threatening
- Moderate: events that require medical treatment but are not immediate life-threatening conditions
- Serious: events that result in death or are life threatening and require medical treatment, including prolonged hospitalization or significant disability/incapacity

Relatedness

For all events observed or reported, the project will further classify them into three categories in relation to the intervention:

- Not related: an event that is reported but not directly related to participation in the intervention
- Possibly related: an event that is observed during an exercise class that is considered likely to be associated with participation
- Definitely related: an event that is observed or reported during an exercise class and is considered directly related to participation.

Adverse Events and Serious Adverse Event (SAE) Reporting Process

We will carefully monitor for unexpected adverse events, as well as the expected outcomes, that participants experience during each online exercise session and outcome assessment, whether or not the events or outcomes are directly related to the study intervention. All symptoms reported by the study participants will be tabulated in a checklist format and recorded by a designated research assistant. When an adverse event is identified, the staff member will report it directly to the Principal Investigator (PI). An Adverse Event Report Form will immediately be completed, filed, and reported to PI.

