The PI will be directly responsible for monitoring and documentation of adverse events during the implementation of all prescribed exercise sessions across the three study conditions. Once the project is implemented, any activities (during a class session or during an assessment session) resulting in participant distress or discomfort, exercise-related side effects, injuries, or falls will be reported immediately to the PI, who will, upon consultation with other members of the team, take appropriate action. This will include consultation with the team's medical expert. The PI will report such incidents immediately to the IRB Chair at ORI. Summary reports of adverse events, and any subsequent IRB action taken as a result of such events, will be routinely provided to the NIA PO and the NIA-appointed Safety Officer.

For each event observed or reported, regardless of setting where the event takes place (i.e., at home or during exercise classes), a designated research assistant will contact the participant within 3 working days, via a telephone call, to ascertain detailed information related to the event. During this phone contact, information about date/time, location, nature of the event, symptoms experienced, and any measures taken for the event will be collected and documented. If necessary, the informant for the study participant will be contacted to verify the information provided by the participant. The recorded event, along with a detailed description, will be tabulated in a checklist format and entered into the project's Adverse Event Log. It will be shared immediately with the PI, who will report, within 3 working days, to the IRB, NIA-appointed Safety Officer, and Project Officer at NIA.

The following summarizes the reporting procedure to be implemented in this project:

- Expedited reporting: All SAEs (including expected and related or possibly related) observed during the active study period will be reported to local IRB and Safety Officer within 3 working days.
 - Routine reporting: All events will be included in routine reports.

Fidelity of intervention delivery

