Throughout the study period, both intervention- and non-intervention-related adverse events will be closely monitored and recorded by research staff and adjudicated by the Principal Investigator. We will classify adverse events in three categories: Mild (i.e., events that require no medical treatment or are not life threatening), Moderate (i.e., events that require medical treatment but are not immediate life-threatening conditions), and Serious (i.e., events that result in death or are life threatening and require medical treatment, including hospitalization, or significant disability/incapacity). For all events observed or reported, we will further classify them into three categories in relation to the intervention: Unrelated (an event that is reported but not directly related to participation in the intervention), Possible (an event that is observed during a class and that is considered likely to be associated with participation), or Definite (an event that is observed or reported during a class and is considered directly related to participation).

Per our IRB protocol, any serious adverse events that we have collected during the entire course of intervention will be reported to the IRB and the project Safety Officer within 48 hours of the reported incident. This will also include unanticipated issues such as prolonged hospitalizations and deaths. Safety analysis will involve tabulating the occurrence of adverse events, including Serious adverse events (deaths and hospitalizations) and unanticipated problems/issues among the three groups. Given the low risk of the trial, no inferential statistical tests are planned for safety.

Statistical software

Statistical analyses will be performed with the use of Stata software (version 17, Stata Corp), SPSS software (version 25, SPSS), and Mplus software (version 8.4, Muthén & Muthén).

Programming plan

All statistical programs used to generate the study results and unidentifiable data will made available upon reasonable request to the PI of this project.

Data Management

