All data collected (self-reports, interviews, recorded study outcome performance ratings or scores) from the project will first be stored in locked filing cabinets in a designated area inside the ORI office building and, after review for completeness and accuracy, will be entered into a secure, password-protected ORI computer network database to be established by the data team staff. Only authorized project staff conducting this project will have full access to the data collected. Participants and informants' responses to the project surveys, interviews, and other forms of data will be coded with a unique numeric identification code. Only designated project staff will have the key to the file cabinets or password to the database and will have access to the data only for status checking or data verification purposes. An Excel data system will be created to track the subjects' status related to recruitment, enrollment, intervention participation, and follow-up assessment. For all raw data, a system file will be created, using the SPSS statistical software, that merges various subsets of data for final analyses. A periodic security check on the data files will be conducted under the supervision of project's statistician. Only the designated data analyst, project biostatistician, and PI will have access to the raw data and analyses.

Timing of Statistical Analysis

To address the primary aim of the study, preliminary and main statistical analyses and evaluation of the trial primary and secondary outcome measures specified in this protocol will begin immediately upon completing the last study participant follow-up at 6 months. To address the secondary aim of the study, analyses and evaluation of trial data will begin immediately upon completing the last study participant follow-up at 12 months.

Adverse Events Reporting

The following summarizes the procedures that will be followed by the investigative team when a participant experiences an adverse event (during the entire course of the study project):

- 1. The participant will be encouraged to call ORI's research staff at [contact] or [contact] (toll free).
- 2. ORI's staff will file an incident report and immediately report the event to the Principal Investigator ([name].).
- 3. The Principal Investigator will inform ORI's IRB administrator ([contact]) and project Safety Officer appointed by NIA of the incident within 48 hours.

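### The plan describes no scheduled question on adverse events or falls for every participant, and events are classified by a Principal Investigator not listed as masked

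*Protocol*

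**What the plan says.** **How events enter the record.** The Protocol's section on the reporting process for adverse and serious adverse events has staff watch for events "that participants experience during each online exercise session and outcome assessment". It continues: "All symptoms reported by the study participants will be tabulated in a checklist format and recorded by a designated research assistant". The later section Adverse Events Reporting, repeated in the SAP, adds a participant-initiated route: "The participant will be encouraged to call ORI's research staff".

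**What happens next.** A research assistant telephones within 3 working days of an event being seen or reported, wherever it occurred. On the informant: "If necessary, the informant for the study participant will be contacted to verify the information provided by the participant".

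**Other staff contact.** Under Intervention adherence and attrition, anyone who misses two sessions in a row is telephoned and asked why. Attention control across intervention groups plans no further contact unless circumstances are special.

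**Who classifies.** Under Adverse events monitoring, events are "closely monitored and recorded by research staff and adjudicated by the Principal Investigator of the study". The reporting-process section adds: "The PI will be directly responsible for monitoring and documentation of adverse events during the implementation of all prescribed exercise sessions", and extends this to all three conditions. The Masking row of the Synopsis names outcome assessors and data analysts only.

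**What is reported.** Under Intervention safety and analysis, in both documents: "Safety analysis will involve tabulating the occurrence of adverse events". This is done by group, with no tests.

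**The concern.** Entry requires reported memory decline. Asking such participants to remember an event and mention it unprompted is a weak way to count falls, and the informant, who could compensate, is brought in only after an event is known. The likely result is a harm table that is too low in every arm.

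A between-arm distortion is possible too, because the output is a plain count per group. If one arm attends more, talks more with staff or reports more readily, it will show more events at the same true risk, and no later step would reveal that.

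Classification raises a separate issue. Severity and relatedness involve judgement, and the person who judges has duties that make knowledge of the arm very likely.

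**Working it through.** The documents give no harm rate, capture rate or safety power, so there is no figure of the plan's to reproduce. The check is mainly a reading of the entry routes, with a short calculation for scale.

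**1. How much time is under observation.** Each arm has 48 sessions of 60 minutes over 24 weeks (Protocol, Intervention and Attention control).
- Class time: 48 × 1 h = 48 h.
- Total time: 24 × 7 × 24 = 4,032 h.
- Share: 48 / 4,032 = 1.2%.

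Most falls would therefore happen unobserved and need a report.

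**2. What reaches an event outside class.**
- *Participant report or call-in*: depends on recall and initiative.
- *Outcome assessments*: staff monitor what happens there, and assessments are held whatever the attendance, with projected completion of 95%, 90% and 85% at 4, 6 and 12 months (SAP Table 2). No question about events since the last visit is described.
- *Missed-session call*: can bring out an injury or illness, but asks about absence, so it misses events that caused none. It stops when classes end at week 24.
- *Informant*: verifies a known event and is not described as a source of new ones.

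Table 1 lists no safety item. It is an outcomes table and the forms are not reproduced, so the supportable statement is that no such question is described.

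**3. What under-capture does to the table.** Recorded participants = n × true risk × capture, with n = 315 / 3 = 105 per arm. True risk and capture are assumptions. At a true risk of 20%, 105 × 0.20 = 21 participants per arm have an event.

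| Assumed capture, arm A vs arm B | Recorded A | Recorded B | Ratio |
|---|---|---|---|
| 60% vs 60% | 12.6 | 12.6 | 1.0 |
| 90% vs 70% | 18.9 | 14.7 | 1.29 |
| 90% vs 50% | 18.9 | 10.5 | 1.80 |

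The ratio is capture A / capture B, so it does not depend on true risk. The spurious difference does. Across true risks of 10% to 40% it is 2 to 8 percentage points in the second row and 4 to 16 in the third. Equal under-capture leaves the ratio at 1.0.

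**4. Whether capture could differ by arm.** Contact time is planned to be equal, and one attendance target of at least 75% (0.75 × 48 = 36 sessions) covers all arms. On the other side, 15% are expected to stop classes, participants and instructors know the arm, and the standard arm is taught without exchange between instructor and participant during exercise whereas the enhanced arm uses interactive tasks. A difference is plausible, but neither document gives evidence of one.

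**5. Classification.** The Principal Investigator is outside the masked roles, trains the instructors and oversees event monitoring in all arms. Logged events go into routine reports, so classification can change an event's severity or relatedness but not its presence.

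**6. Two wording problems in the same Protocol sections.**
- Under Relatedness, the middle category requires that the event be seen during a class. An event outside class has no route into it, so the relatedness table also depends on where the event occurred.
- Classification of Adverse Events covers the 6-month active period, whereas Adverse events monitoring and Adverse Events Reporting cover the whole study. The status of events in weeks 24 to 48 is unclear.

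**The case against.** The strongest reply is that capture is broader than spontaneous reporting. Staff monitor at assessments held regardless of attendance, including for people who stopped classes and at 12 months. Absentees are telephoned, and events at home are in scope once reported. This stands against a reading that a reader might reach, namely that events are recorded only if seen or volunteered and that those of non-attenders are lost. It does not supply a question put to everyone.

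A reader might also infer that the by-arm table is biased. The documents do not support that. Memory loss alone lowers counts in all arms, contact time is planned to be equal, and any ratio away from 1.0 rests on a capture or attendance gap for which the documents give no figure.

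Nor do they say that the Principal Investigator is unmasked; that is a strong inference from the Masking row and the assigned duties. Severity rests largely on fairly objective facts such as treatment, threat to life, death and disability. The Principal Investigator consults a medical expert, and a funder-appointed Safety Officer receives reports. These points limit the scope for biased classification, though relatedness remains a judgement.

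Finally, safety is descriptive in a trial described as low risk, and no endpoint or power figure changes. That is correct and limits the weight of the point.

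**Conclusion.** The point holds in a limited form. No scheduled query, identical across arms, is described for adverse events or falls. With entrants selected for memory decline, under-counting in all arms is likely. Its size cannot be derived from the documents; under an assumed 60% capture, 40% of affected participants would be missing.

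Distortion between arms is conditional. The ratio is 1.0 if capture is equal, and 1.29 or 1.80 under the assumed gaps of 90% vs 70% and 90% vs 50%. Those two figures are illustrations and should not be cited as estimates for this trial.

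Classification by someone not listed as masked can affect severity and relatedness categories, but not whether a logged event is counted. The relatedness definition and the classification window need reconciling whatever is decided on the rest. No efficacy conclusion is affected.

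**What to change.** - **Ascertainment.** Add one identical checklist to the participant survey and the informant questionnaire already collected at 4, 6 and 12 months (Table 1). Ask about any fall, injury, new pain, medical visit or hospital stay since the last assessment. Return it to the safety research assistant, so that the blinded assessor does not see it.
- **Reporting.** Tabulate participants with at least one event per arm from this source, and show class-observed events separately.
- **Classification.** Where feasible with existing staff, classify severity and relatedness from narratives with arm-identifying details removed, including names of forms or cognitive tasks. The medical expert is a possible choice, but the documents do not state that person's masking or availability.
- **Wording.** Reconcile the 6-month classification window with the whole-study sections, and state whether an event outside class can fall in the middle relatedness category.
- **If collection is over.** The documents cite a published trial report, so this may be the case. Log narratives can still be reclassified with the arm removed, class-observed events can be separated, and the method of ascertainment can be stated beside the harm table.

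The cost is one survey page, preparation of masked narratives, and higher recorded counts. Recall error remains, because the recall periods are 4, 2 and 6 months; the informant page reduces this but does not remove it. No new visits are needed, and sample size and power do not change.

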To augment our paper-and-pencil measures, we will also employ Cogstate (cogstate.com), a set of customized, computerized tasks taxing verbal learning, including (a) International Shopping List Task plus a recall (the number of correct responses is used as the unit of measurement); (b) attention (Identification [speed of performance]); (c) working memory (One Back Task [speed of performance]); (d) visual recognition memory/attention (One Card Learning Task [accuracy of performance]); and (e) executive function (Groton Maze Learning Task [accuracy of performance]). These assessments are performed on a desktop computer and administered according to guidelines. The test session takes about 45 minutes to complete, with a practice before every task. Similar to the paper-and-pencil tests, a composite cognitive score will be calculated from these computerized cognitive tests.

Physical Performance

Functional Reach. In an upright standing position, this measure (measured in inches) assesses the maximal distance the participant can reach forward, beyond arm's length, while maintaining a fixed based of support in the standing position.²⁷

Short Physical Performance Battery (SPPB). This measure includes (1) increasingly challenging standing balance tasks (side-by-side stand, semi-tandem stance, tandem stance), (2) a 4-meter walk (gait velocity) at normal pace, and (3) repeated chair stands (leg strength).²⁸ A single SPPB measure is used, with the scale score ranging from 0 points (worst physical function) to 12 points (best physical function).

Timed Up&Go (TUG) test. The TUG measure²⁹ is recorded in seconds (the time taken by an individual to stand up from a standard armless chair, walk a distance of 3 meters, turn, walk back to the chair, and sit down).

Covariates

There are no pre-specified covariates in this study.

Tertiary measures

These measures include the (a) Everyday Cognition scale,³⁰ (b) Pittsburgh Sleep Quality Index,³¹ (c) Geriatric Depression Scale,¹⁷ and (d) EuroQol EQ-5D for health-related quality of life.³² These measures, described below, are included in a paper survey completed by participants.

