Intervention classes will be closely monitored by research staff throughout the study period. Session-by-session attendance of the study participants will be recorded by research staff, regardless of participants' participation status, and this information on exercise adherence rate will be used as an indicator of intervention adherence across the three intervention groups. For each intervention group, there will be a total of 48 exercise classes to be completed over the 24-week intervention period. Accordingly, the average intervention adherence rate will be calculated as follows: number of intervention sessions attended during the 24 weeks divided by total number of sessions prescribed for the study, reported as a percentage.

Baseline measures

At baseline, demographic and other information about age, sex, ethnicity/race, income, education, living arrangements, medical conditions, health status, habitual physical activity, ³⁴ and residence location will be collected via a survey questionnaire. Body weight, assessed by a medical scale, and height, measured by with a ruler fixed on a wall, will also be ascertained. These data will be used to describe study population characteristics at baseline.

Statistical Analysis Plan (SAP)

Study aims

The study has the following primary and secondary aims.

Primary aim

To determine whether a cognitively enhanced tai ji quan intervention, in comparison to a standard tai ji quan intervention and an exercise stretching control, is more effective in improving global cognitive function and dual-task walking performance among community-dwelling older adults with MCI.

Primary hypothesis: We hypothesize that, at 6 months, cognitively enhanced tai ji quan training will result in greater gains in the primary outcomes of global cognition and dual-task gait performance than either standard tai ji quan or stretching control.

Secondary aim

To determine whether the effect resulting from the acute intervention phase can be sustained 24 weeks after training stopped.

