 - Participants' characteristics ascertained at baseline will be compared across intervention groups using independent samples or Wilcoxon rank sum tests, as appropriate, for continuous variables and a chi-square or Fisher's exact tests, as appropriate, for categorical variables. Although no significant differences are expected due to the randomized intervention assignment and the relatively large sample size, any variables found to be significantly different will be noted and accounted for, by controlling for them as covariates in supplements to the main analyses.
- *Time-specific and change scores*. Scores at each follow-up and change in mean scores from baseline at 24 weeks, by intervention group, for all outcome measures will be calculated and presented.
- *Intervention adherence, attrition, and retention*. Class attendance data will be calculated as the average number of scheduled intervention sessions (48 total) attended by participants across intervention groups. Study attrition and retention rates will also be calculated and reported, by intervention group, as the number of participants who completed the 24-week intervention and those who completed all scheduled study follow-up assessments.

Analysis populations

Efficacy analyses. The effect of intervention on the co-primary study outcomes will be evaluated using an intention-to-treat approach in which participants will be analyzed according to randomization assignment. A modified intention-to-treat analysis will be conducted that includes all participants who have undergone randomization and have completed all study follow-up assessments, regardless of their participation adherence status. Finally, a per-protocol analysis will include participants in the intention-to-treat population who have an overall class attendance rate of $\geq 75\%$ (out of the total planned 48 intervention class sessions) of their assigned exercise intervention.¹⁰

Co-primary endpoint analyses

To test the *Primary hypothesis*, we plan to use a generalized linear mixed model with random intercepts and fixed treatment effects for the primary outcomes. Specifically, we will determine the intervention effect through an analysis of a 3 (Group) by 3 (Time) mixed-effects model with repeated measures (follow-up time point) on the second factor (i.e., outcome measures assessed at baseline, 4 months [mid-point], and 6 months [intervention termination]).

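### Supplementary covariates are picked by baseline significance tests, so the adjusted model is set by chance imbalance and not by prognosis

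*Protocol*

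**What the plan says.** The rule is in the Protocol's Statistical Analysis Plan, Descriptive analyses, Comparability of intervention groups, and is repeated in the separate SAP. Baseline characteristics are "compared across intervention groups using independent samples or Wilcoxon rank sum tests, as appropriate, for continuous variables" and by "a chi-square or Fisher's exact tests, as appropriate, for categorical variables". The plan remarks that "no significant differences are expected due to the randomized intervention assignment and the relatively large sample size", and then commits that "any variables found to be significantly different will be noted and accounted for, by controlling for them as covariates", in analyses that supplement the main ones.

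The plan does not state the significance level for these tests, the variables to be tested, the pairs of arms to be compared, any control for multiplicity, or how a flagged variable enters the model.

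The Protocol's Covariates section says: "There are no pre-specified covariates in this study". The synopsis says the same for the primary and secondary endpoints. Baseline measures lists "age, sex, ethnicity/race, income, education, living arrangements, medical conditions, health status, habitual physical activity", and then residence location, weight and height. Treatment of noncompliance and missing data names age, sex, education, MMSE, number of chronic conditions and depression as complete baseline variables, but only as predictors for imputation.

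**The concern.** If randomisation was carried out properly, every baseline difference between arms arose by chance. A p-value for that difference says nothing about whether the variable predicts MoCA or dual-task cost, so it cannot show which variables are worth adjusting for. The content of the adjusted model is therefore unknown until the baseline p-values have been seen, although the plan describes itself as pre-specified.

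The reassurance drawn from sample size does not help. The false-positive rate of a valid test is its nominal level at any sample size.

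The continuous-variable tests also do not fit the design. An independent-samples test or a rank sum test compares two groups. With three arms it must be repeated over pairs, which raises the chance of a flag per variable.

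At stake is how the supplementary adjusted results can be read. They would depend on an accidental choice of covariates, while a variable that does predict outcome would usually be left out.

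**Working it through.** **The plan's own figure.** There is none to reproduce. The plan gives no error rate for this rule, only the expectation of no significant differences.

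**Inputs.**
- Three arms, 1:1:1, 315 randomised, so 315 / 3 = 105 per arm (Study design; Method of randomization).
- 12 characteristics: the nine quoted above, plus residence location, weight and height (Baseline measures).
- Two-sided 5% level. This is an assumption. It is the level the plan gives for secondary and tertiary outcomes.
- Four continuous and eight categorical variables. This split is an assumption, because the documents do not fix it.
- Independence between variables. This is an assumption and is relaxed below.

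**Chance that one variable is falsely flagged.** 400,000 simulated trials with no true difference and 105 per arm gave:
- one three-arm test: 5% by definition
- two pairs (enhanced arm against each comparator): 9.0% (0.0896)
- all three pairs: 12.2% (0.1216)

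**Chance of at least one false flag among the 12.** The formula is 1 minus the product of (1 - p) over the variables.

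| Reading of the plan | Calculation | Result |
|---|---|---|
| One three-arm test per variable | 1 - 0.95^12 | 46% |
| 4 continuous on two pairs, 8 categorical on a three-arm test | 1 - 0.9104^4 x 0.95^8 | 54% |
| 4 continuous on three pairs, 8 categorical on a three-arm test | 1 - 0.8784^4 x 0.95^8 | 61% |
| Three pairs on every variable | 1 - 0.8784^12 | 79% |

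The expected number of false flags is 12 x 0.05 = 0.6 in the first row and 4 x 0.1216 + 8 x 0.05 = 0.89 in the third. The plan expects none.

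**Sensitivity.**
- With three to five continuous variables, the third row runs from 57% to 63%.
- With a common correlation of 0.2 between variables, the first and third rows become 43% and 57%.
- With a correlation of 0.5, they become 33% and 45%. That correlation is high for variables as different as sex, ethnicity and location.
- If MMSE and the 14 outcomes of Table 1 were also tested at baseline (12 + 1 + 14 = 27 variables), three-arm tests throughout would give 1 - 0.95^27 = 75%.

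**Chance that a given factor is adjusted for.** This is the per-variable figure: 5%, 9% or 12%, according to the tests used. How strongly the factor predicts outcome does not enter the calculation.

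**Whether adjustment moves the result.** The planned model has baseline as a repeated outcome, random intercepts and Group by Time. Primary and secondary outcomes are multiply imputed, so each analysed data set is complete. In such a model the Group-by-Time contrasts are estimated from differences within participants. A covariate that is constant over time cancels out of those differences. A simulation with 89 per arm and a deliberately imbalanced, prognostic age gave a 24-week contrast of 1.479 (SE 0.417) both without age and with age as a main effect. With age-by-time added, the contrast became 1.446 (SE 0.417). A flagged variable could therefore be controlled for as a main effect and change nothing in the comparison of interest.

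**The case against.** Several stronger readings are tempting, and the documents do not support them.

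- **That the rule will usually produce a flag, at a rate near 79%.** This needs three pairwise tests on all 12 variables. The plan names two-sample tests for continuous variables only. Chi-square and Fisher's tests can compare three arms at once, and many of the listed items are naturally categorical. The phrase about independent samples also lacks its noun, so it may be loose wording and not a decision to test in pairs. With one three-arm test per variable the figure is 46%.
- **That important baseline factors are ignored.** Age, sex and education are factors in the planned subgroup models. With MMSE, they are also imputation predictors. The baseline value of each outcome is already in the model. What is missing is a fixed adjustment set. The documents also do not establish that these four variables predict change at 24 weeks.
- **That adjusted results will shift with each chance imbalance, or that a fixed set will bring precision.** Neither follows if covariates enter as main effects only, as shown above.
- **That the primary conclusions are at risk.** The rule is confined to supplements. The primary analysis is explicitly unadjusted.

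These arguments limit the size of the point. They do not defend the rule. Even one three-arm test per variable selects on chance, and the plan gives no reason for choosing covariates in that way.

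**Conclusion.** The concern holds as a minor point. The plan selects supplementary covariates by a criterion unrelated to prognosis, and it names two-sample tests for continuous variables in a three-arm trial. Under the stated assumptions (5% level, 12 variables, independence), the chance of at least one false flag is 46% with three-arm tests throughout. It is about 54% to 61% with the assumed mix of four continuous and eight categorical variables. Positive correlation between variables lowers these figures, and testing more variables raises them. The documents fix neither the level nor the list of variables, so the range should be quoted and not a single value. The 5% to 12% chance that a particular factor is adjusted for needs only the assumed level and the choice of pairs. The effect is limited to supplementary analyses.

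**What to change.** In both documents, delete the baseline significance tests and the covariate rule that depends on them. Keep the descriptive table by arm.

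In their place, pre-specify one supplementary model for each primary outcome, adjusted for age, sex, education and baseline MMSE. State how the covariates enter: each with its interaction with time, or as covariates in an analysis of change at 24 weeks. Do not promise a precision gain beyond what these covariates explain in change.

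Both documents cite a published report of the trial, so some analyses have probably been done. In that case, label any adjustment chosen by significance as data-driven, report the fixed-set model beside it, and label that model post hoc.

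The cost is a change of wording and one extra model specification. The four covariates are already collected and are listed in the plan as complete, and the baseline tests no longer have to be run.
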